It was estimated that approximately 50% of these are for new infestations in children, i.e. the remaining 50% of units are for adults or infants or either for retreatment after failure to cure or are additional purchases as part of a 2x application treatment regimen. Therefore, the number of new cases of head louse infestation is actually approximately 24,572 per week. And as there are approximately 5.4 million children in the highest “at risk” age group in the UK (4-13 years) this means that approximately 0.455% of children become infested each week.

In order to relate these data to this study it is known that the child population of Cambridgeshire in the “at risk” age group is about 51,000, which means that approximately 232 cases of head louse infestation occur in the whole of Cambridgeshire each week.

Two approaches to the study size estimation were considered, a straightforward

comparative study of two groups or a cross-over study using a survival analysis consideration, with each participant acting as his or her control. The arguments in favour of the cross-over model appear stronger in that smaller numbers of participants can be engaged, to minimise exposure to the new preparation, and it also offers internal controlling, with each participant acting as his or her control (with the assumption that the individual's risk remains more or less constant over the relatively short time of the study). The risk factors for each individual are sufficiently unknown that randomisation alone may not wholly address any disparity in infestation risk due to social and family circumstances, especially in a relatively small study cohort. Therefore, self-controlling for each individual is an attractive option to avoid any skew resulting from these unknown factors. By using a cross over study it would be possible to use a survival analysis approach in relation to time to first infestation (see **Analytical Methods**, below).

Calculations were made to investigate the possibility of using the cross-over estimations to limit participant numbers, for example to say 15 per group. However, when the "incidence" figures above were applied, it was found that it would be likely it would be impossible to make a reliable comparison between the product and placebo because of the possible low rate of infestation in the population as a whole.

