In order to partially address the problems outlined above it is planned to mostly recruit from contacts, obtained from previous clinical studies, who have expressed an interest to take part in a study of this type. This group is known to be more at risk. Therefore, based on past study data relating to when people have contracted lice after study treatments, there is a reasonable expectation of an infestation rate of between 3 and 5 instances of reinfestation per year for each person in that group, i.e. a risk of about 3.6-4 possible reinfestation events per week for the whole study population. This doesn't mean that they will get lice but rather that they could come into contact with someone who does have them and lice could therefore be passed to them.

An estimation of sample size was made using conventional "survival analysis" calculations and the table below is taken from http://www.stattools.net/SSizSurvival_Pgm.php.

The table of sample size for 2 survival ratios is applicable to the common situation where the probability of Type I error $\alpha = 0.05$ (95% confidence) and power = 0.8 (80% power). In conventional survival analysis terms it assumes that the sample size in each of the two arms is the same, which in this case is certainly correct because each individual participates in both treatment arms sequentially.

The rows and columns represent the anticipated proportions of participants remaining louse free in each of the two treatment arms, and each cell is the total sample size (both treatment arms together) for that row/column combination. The shading covers the anticipated range of outcomes. These estimations of size that are proposed for this study appear to be at around the lower bound of population size required for the 30-35% difference in outcome between treatments necessary to detect superiority (range 62-90 participants) using a cross-over model, thus fulfilling the preferred aim of minimising the number of participants in the study.

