For a randomise-by-individual approach, assuming a confidence level of 95% and a power of 80%, and anticipating the expected non-infestation rates to be 65% for Octanediol 1% Solution and 30% for the placebo, the required sample size is therefore estimated as 34 subjects per treatment. However, this study will operate a “hybrid” randomization in that only one person from each household will be randomized (index case) and all others in the house will be offered treatment when infestation arises but will continue to potentially act as a source of reinfestation. This approach reduces possible confounding issues of enrolling all members, in which some households will have all members on one intervention but others will have a mixture of active and placebo interventions. Therefore, for each participant on each arm of the cross-over the familial risk of reinfestation should be similar in this respect.

Sample size table for 2 hazard ratios in survival analysis

| | 0.05 | 0.10 | 0.15 | 0.20 | 0.25 | 0.30 | 0.35 | 0.40 | 0.45 | 0.50 | 0.55 | 0.60 | 0.65 | 0.70 | 0.75 |
|------|------|------|------|------|------|------|------|------|------|------|------|------|------|------|------|
| 0.10 | 496 | | | | | | | | | | | | | | |
| 0.15 | 173 | 963 | | | | | | | | | | | | | |
| 0.20 | 99 | 295 | 1414 | | | | | | | | | | | | |
| 0.25 | 69 | 155 | 406 | 1826 | | | | | | | | | | | |
| 0.30 | 53 | 100 | 203 | 504 | 2186 | | | | | | | | | | |
| 0.35 | 43 | 73 | 127 | 245 | 588 | 2486 | | | | | | | | | |
| 0.40 | 36 | 57 | 90 | 149 | 280 | 656 | 2723 | | | | | | | | |
| 0.45 | 32 | 47 | 68 | 103 | 167 | 307 | 708 | 2894 | | | | | | | |
| 0.50 | 28 | 39 | 54 | 77 | 114 | 181 | 326 | 743 | 2997 | | | | | | |
| 0.55 | 26 | 34 | 45 | 60 | 83 | 121 | 190 | 338 | 761 | 3032 | | | | | |
| 0.60 | 24 | 30 | 38 | 49 | 65 | 88 | 126 | 195 | 343 | 761 | 2999 | | | | |
| 0.65 | 22 | 27 | 33 | 41 | 52 | 67 | 90 | 128 | 195 | 339 | 744 | 2897 | | | |
| 0.70 | 21 | 25 | 30 | 36 | 43 | 54 | 69 | 91 | 127 | 192 | 328 | 711 | 2727 | | |
| 0.75 | 20 | 23 | 27 | 31 | 37 | 44 | 54 | 68 | 89 | 123 | 183 | 310 | 660 | 2490 | |
| 0.80 | 19 | 22 | 24 | 28 | 32 | 37 | 44 | 54 | 66 | 86 | 116 | 171 | 284 | 592 | 2186 |
| 0.85 | 18 | 20 | 23 | 25 | 28 | 32 | 37 | 43 | 52 | 63 | 80 | 107 | 154 | 250 | 508 |
| 0.90 | 18 | 19 | 21 | 23 | 26 | 28 | 32 | 36 | 42 | 49 | 59 | 73 | 95 | 133 | 209 |
| 0.95 | 17 | 19 | 20 | 21 | 23 | 25 | 28 | 31 | 34 | 39 | 45 | 53 | 64 | 81 | 108 |

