This estimate of the likely numbers in relation to application of the Octanediol 1% Solution active material for 6 weeks followed by placebo for 6 weeks assumes that the potential rate of contact and reinfestation is more or less linear so that, where it was estimated from past data that a likely reinfestation rate would be approximately 4 per week for the whole population, the possible number of new cases would be 24 over the 6 weeks of one half term, or 12 cases per treatment if neither had any effect. However, if the test preparation is effective this number of cases could be reduced by approximately 60% resulting in 5 cases. This difference offers essentially similar powering to that of a parallel group calculation, although the statistical significance would be reduced overall if the reinfestation rate were to be no greater than 4 per week.

Analytical Methods:

The primary endpoint analysis is the comparison between the Octanediol 1% Solution and placebo in the frequency of not developing an infestation, with the difference between the two study treatment arms tested using the "intention-to-treat" population. Secondary endpoint analyses will be the frequency (number) of instances of reinfestation and safety of the product and participant acceptance.

Analyses will be conducted based on both the "intention-to-treat" and the "per-protocol" populations.

As this is a cross-over study with equal numbers in each treatment arm it is appropriate to analyse efficacy using a Kaplan-Meier survival analysis. This analysis will compare the time to first infestation for each individual in each arm of the crossover, in which the time to first infestation is taken as the "survival" endpoint. This will essentially address the three first analytical tasks set out in section 3.3, although point 1. will also be addressed in other analyses.

It is not considered that censoring will present as a major issue during the first half term period and, if it does occur at all, right censoring from the second half term is the likely outcome. For these data it would be appropriate to use the log-rank test to analyse in relation to time to first infestation. Comparison of the "survival" curves would probably be more appropriate in this case using the Brand and Altman approach and hazard ratio curves rather than conventional Kaplan-Meier curves (Bland and Altman, *BMJ*, 2004, 328, 1073).

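### The log-rank test named for time to first infestation treats the two arms as separate people although every child is in both, so it is conservative and gives up within-child precision

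*Protocol*

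**What the plan says.** Section 3.4, Analytical Methods, sets out the efficacy analysis: "As this is a cross-over study with equal numbers in each treatment arm it is appropriate to analyse efficacy using a Kaplan-Meier survival analysis". It compares time to first infestation for each individual in each arm, is said to cover the first three tasks of section 3.3 (which include the comparison with placebo), and "it would be appropriate to use the log-rank test to analyse in relation to time to first infestation". Pairing, clustering by participant, frailty, period and sequence are not mentioned for this analysis.

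The sample-size part of the same section explains the design. Because each child's risk factors are largely unknown, "self-controlling for each individual is an attractive option to avoid any skew resulting from these unknown factors". On arm sizes it says of the sample-size table that "it assumes that the sample size in each of the two arms is the same", and regards this as met "because each individual participates in both treatment arms sequentially".

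Section 3.4 also names two paired tests. McNemar's test on the binary outcome could be added if no censoring occurs. The Wilcoxon signed rank test is specified firmly, but for the number of infestations per participant (task 4).

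**The concern.** The log-rank variance is derived for two groups of different people. Here the same children form both curves. The reason given for the method, equal numbers per arm, has no bearing on that. If a high-risk child tends to be infested early under both products, the two curves are positively correlated. The variance of their difference is then smaller than the log-rank assumes.

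The protocol therefore gives a reason for the cross-over that its main test does not use. At stake are a p-value and interval that do not have their nominal meaning, and power in a trial of 68 children that may see few infestations. Section 3.4 itself expects reduced significance if the rate is no greater than 4 per week.

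**Working it through.** **1. The protocol's own figure.** Inputs from section 3.4: "assuming a confidence level of 95% and a power of 80" per cent, "anticipating the expected non-infestation rates to be 65% for Octanediol 1% Solution and 30% for the placebo". The two-sided Freedman log-rank formula reproduces the result:
- HR = ln 0.65 / ln 0.30 = 0.358
- events = (1.96 + 0.8416)² × ((1 + 0.358)/(1 − 0.358))² = 35.1
- total = 35.1 / 0.525 = 66.8, where 0.525 is the mean event probability, 1 − (0.65 + 0.30)/2

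This is the table cell of 67, and "the required sample size is therefore estimated as 34 subjects per treatment". The formula is for independent groups, so the sizing, like the test, makes no use of pairing.

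**2. Direction of the error.** Let φ be the within-child correlation of the binary outcome (an assumption; the protocol gives none). For 65% vs 30%, per child:
- variance if independent: 0.65×0.35 + 0.30×0.70 = 0.4375
- true variance: 0.4375 − 2φ√(0.2275×0.21) = 0.4375 − 0.437φ

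The independent-groups standard error is too large by a factor of 1.12 (φ = 0.2), 1.20 (φ = 0.3) or 1.29 (φ = 0.4). Under no effect the variance ratio is 1 − φ, so a nominal 5% test rejects in 2.8%, 1.9% or 1.1%. The error is conservative.

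**3. Size for time to first infestation.** Simulation inputs:
- From the protocol: 68 children, two six-week periods, weekly detection, sequences 34/34, and a hazard ratio of 0.4 (the expected 60% reduction).
- Placebo rate, two cases from section 3.4. At 4 events per week for the whole group, the six-week cumulative hazard is 24/68 = 0.353 (70% louse free). At 5 per person-year it is 5×6/52 = 0.577 (56% louse free).
- Assumed: gamma-distributed risk between children, mean 1, with coefficient of variation (CV) from 0 to 1.5.

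The comparator is a log-rank score test stratified by period with participant-clustered variance. Power, log-rank vs comparator:

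| CV of risk | 4 per week | 5 per person-year |
|---|---|---|
| 0 | 65% vs 65% | 84% vs 83% |
| 0.5 | 63% vs 64% | 80% vs 81% |
| 1.0 | 55% vs 61% | 68% vs 76% |
| 1.5 | 40% vs 52% | 50% vs 67% |

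A repeat with 4,000 trials per setting agreed within 2 points. The Monte Carlo standard error is about 0.8 points at 60%, so one-point differences are noise. Both columns fall with CV partly because risk concentrates in fewer children. At 4 per week the expected first infestations on placebo drop from 68×(1 − e^−0.353) = 20 at CV 0 to 68×(1 − (1 + 2.25×0.353)^(−1/2.25)) = 16 at CV 1.5. The gap within each cell is the cost of ignoring pairing.

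The true type I error of the log-rank is about 5% at CV 0, 2 to 3% at CV 1.0 and 1 to 2% at CV 1.5. The comparator stays near 5%.

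**4. At the planning rates.** With 65% and 30% held as the overall proportions and log-normal risk, the log-rank on 68 children has at least 99% power, against 96–100% for a participant-stratified log-rank. With gamma risk at CV 1.0 and the overall proportions free to shift, it is 90% vs 95% for the clustered test.

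**The case against.** **The error is conservative, and at the planning rates it hardly matters.** Both statements are right: a positive log-rank result would not be undermined. But section 3.4 gives 65% and 30% as rates over a school term, while each treatment period is six weeks. The contact rates in the same section give fewer events, and there the loss is real if children differ in risk.

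**The spread of risk is unknown and may be small.** Most participants come from one known higher-risk group, which could narrow it. At CV 0.5 or below the two tests differ by about a point. This stands, and it is why the range starts at zero.

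**Paired tests are already named.** A reader might infer that the protocol contains no paired analysis; that would be wrong. But McNemar's test is optional and depends on there being no censoring, the Wilcoxon signed rank test serves only the infestation counts, and neither allows for period.

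**Detail of this kind may sit in a statistical analysis plan.** One may exist and was not available. The protocol, however, does not leave the choice open: it names the log-rank test and calls it appropriate.

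Two stronger readings are tempting. One is that the benefit of the cross-over is lost altogether. It is not: 68 observations per product, with pairing ignored, give about 99% power at 65% vs 30% by the two-proportion formula, against 84% for a parallel 34 vs 34. The other is that ignoring period could inflate false positives. That needs clearly unequal sequences together with a strong period difference. The protocol randomises in balanced blocks with at least 34 per group. With 34/34 started, drop-out of 2 vs 8 before period 2 and period-2 risk one third of period 1, the log-rank rejects a true null in only 4.4–4.6%.

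**Conclusion.** The point holds in a limited form. The named test does not fit the data the design produces and contradicts the self-control rationale. When children differ in risk, its p-values and intervals are conservative. The cost is nil to about one point of power at CV 0–0.5, 6 to 8 points at CV 1.0 and 12 to 17 points at CV 1.5, for a hazard ratio of 0.4 at the protocol's lower event rates. At the planning rates power is ample with either test.

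These figures rest on an assumed gamma distribution of risk and an assumed CV. The direction of the error does not depend on the distribution, only on positive correlation within child, which is the protocol's own premise. This should be fixed, but it does not threaten the validity of a positive result.

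**What to change.** In section 3.4, Analytical Methods, replace the ordinary log-rank test by one firm paired analysis of time to first infestation within each six-week period. A suitable form is a Cox model or log-rank score test stratified by period, with robust variance clustered on participant. Use every period that a participant started, and report the hazard ratio with its 95% confidence interval. Keep Kaplan-Meier curves by product for display. The choice should not depend on whether censoring occurs, and should be fixed before unblinding.

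Other paired forms would also serve, such as a participant-stratified log-rank with allowance for period, or a period-adjusted paired test on the binary endpoint. Stratifying by participant costs more if children do not differ: 72% vs 77% power for the ordinary log-rank at 4 infestations per person-year and a 60% reduction.

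The cost of the clustered version is revised wording and a little standard code, with no new data or participants. If children do not differ in risk, power changes by about one point or less.

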3.1.2 Efficacy

The primary endpoint is the frequency of not contracting an infestation by head lice during the course of the study, indicated by no evidence of active head louse infestation.

The main secondary endpoint will be comparison of the frequency (number) of instances of reinfestation.

The other secondary endpoints are the safety and acceptability of the Octanediol 1% Solution preparation in regular use.

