However, if no censoring occurs, it may be more appropriate, because the primary outcome measure is no evidence of active head louse infestation, that the primary analysis method could additionally use the McNemar's test on these binary outcome (evidence/no evidence of active head louse infection during the treatment period) data as a simple method to address point 1. of section 3.3, to answer the question as to whether the Octanediol 1% Solution is able to prevent establishment of a head louse infestation.

In addressing point 4. of section 3.3, which may potentially result in a ranked variable, from how many times each individual becomes infested over the course of each arm of the crossover, the Wilcoxon signed rank test will be used for the paired data derived from the time spent in each arm of the study by each participant.

Because this is a cross-over study there will be no conventional comparison of difference between groups in baseline characteristics. However, the two arms will be tested for comparability of some baseline characteristics, such as presence of infestation, and presence of infestation in other household members at the start of the study and at the commencement of the "wash-out" cross-over treatment. For these comparisons, and comparisons of safety, and acceptability data will be tested using Fisher's exact test for yes/no variables and the Wilcoxon signed rank test for paired data, or Mann-Whitney U test for unpaired, ranked variables.

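### The binary primary endpoint has no fixed test: the implied default is an unpaired log-rank test, and the paired McNemar test is optional and tied to the absence of censoring

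*Protocol*

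**What the plan says.** Protocol 3.1.2 defines the endpoint: "The primary endpoint is the frequency of not contracting an infestation by head lice during the course of the study". The Analytical Methods part of 3.4 says that the two products will be compared "in the frequency of not developing an infestation, with the difference between the two study treatment arms tested using the 'intention-to-treat' population". That sentence fixes the population and names no test.

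The same part then turns to a different variable, time to first infestation in each arm of the cross-over. It calls Kaplan-Meier analysis and the log-rank test appropriate, with no stratified or paired version named, and says that a hazard-ratio comparison would probably suit better. The survival analysis is expected to deal with the first three tasks listed in 3.3.

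On censoring it states: "It is not considered that censoring will present as a major issue during the first half term period". It adds that any right censoring would probably come from the second half term. McNemar's test enters last, as something the primary analysis could use in addition, "if no censoring occurs, it may be more appropriate, because the primary outcome measure is no evidence of active head louse infestation".

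**The concern.** A primary analysis should be one test, chosen in advance and matched to the endpoint. Here the only test named for the yes/no outcome is optional and depends on a feature of the observed data. The default tests another quantity and treats the two periods of one child as two independent samples. Yet 3.4 justifies the cross-over by self-control within each child, because individual risk is too poorly known for randomisation alone to balance it in a small cohort.

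Two things are at stake: whether the headline result can depend on a choice made once the data are known, and whether the pairing that motivated the design is used at all.

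**Working it through.** **Inputs from the protocol.** 68 participants, each with two fixed 6-week periods, so 136 person-periods (1.1, 1.4). Planning rates: "anticipating the expected non-infestation rates to be 65% for Octanediol 1% Solution and 30% for the placebo". Error rates: "assuming a confidence level of 95% and a power of 80" percent; two-sided testing is my assumption. Result: "the required sample size is therefore estimated as 34 subjects per treatment". No dropout rate is given.

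**The plan's own figure reproduces.** With Freedman's log-rank formula:

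- HR = ln(0.65)/ln(0.30) = 0.358
- events = (1.960 + 0.842)² × ((1 + 0.358)/(1 − 0.358))² = 35.1
- total N = 2 × 35.1/(2 − 0.65 − 0.30) = 66.8, that is 67, which is the table cell; 34 per treatment

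The sample size is not in dispute. It rests on an unpaired log-rank comparison, which supports reading that test as the implied default.

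**Reading 1: censoring in the ordinary survival sense.** Follow-up stops at week 6, so a child still louse-free then is right-censored. That state is also the primary endpoint's success.

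- At 65% and 30%: 68 × (0.65 + 0.30) = 64.6 of 136 periods (48%).
- At the low and high ends of the planning ranges (60% with 25%, 70% with 35%): 68 × 0.85 = 58 and 68 × 1.05 = 71 of 136.
- At the case counts in 3.4: these are 12 versus about 5 per treatment in one half term. My doubling over both half terms, with the 60% reduction, gives 24 versus 9.6. Then 136 − 33.6 = 102.4 periods (75%) are censored.
- No censoring would need every child infested on both products. At the planning rates, with independence, that probability is 0.35^68 × 0.70^68, about 3 × 10⁻⁴².

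On this reading the remark that censoring is no major issue is wrong, in the first half term as well as the second.

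**Reading 2: censoring means dropout only.** The chance of no dropout among 68 is (1 − d)^68. The values of d are assumptions.

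| Assumed dropout d | Chance of none among 68 |
|---|---|
| 1% | 50% |
| 2% | 25% |
| 5% | 3% |
| 10% | 0.08% |

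**Does the choice of test matter?** I simulated 68 complete pairs with weekly assessment, two-sided 5%, and assumed latent within-person correlation of 0, 0.3 and 0.6. McNemar's test is the chi-square form unless stated.

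- *No product effect.* The log-rank test rejects in about 5% with independent periods and about 0.4–3% at correlation 0.3–0.6. McNemar's stays near 5%. Rejecting if either is significant gives about 5–7%.
- *65% versus 30%.* Both tests have about 98–100% power. Exact McNemar power with independent periods is about 98%.
- *24 versus 9.6 infestations.* At correlation 0.3–0.6 McNemar's gains about 4–6 points over the log-rank test. The exact form is itself conservative, gives back part of this gain, and at 0.3 gives back all of it.
- *65% versus 45%.* The two tests reach different verdicts in about 7% of trials with independent periods and up to about 15% at correlation 0.6.

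**The case against.** The best defence has four parts.

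*The condition is realistic.* A reader might infer that the no-censoring condition can never hold. The document does not support that. By allowing that censoring might not happen at all, and by placing it in the second half term, 3.4 suggests that loss to follow-up was meant. McNemar's test needs complete pairs, which may be why the authors tied it to that condition. This stands. It does not rescue the rule: 2.3.4 and 2.3.7 provide for several kinds of withdrawal, 3.2 keeps premature terminations in the intention-to-treat population, and a single dropout would remove the matching test.

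*There is a default.* A reader might infer a free choice between rival tests. The text offers McNemar's as an addition, not a replacement, and gives the first three tasks to the survival analysis. That also stands. But the default addresses time to infestation rather than the stated frequency, and every option is worded as something that would, may or could be appropriate.

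*The endpoint is attributable to a product.* The phrase "the frequency of not contracting an infestation by head lice during the course of the study" covers both products, so a reader might conclude that the endpoint belongs to neither. The Analytical Methods text ties the binary outcome to the treatment period, which resolves this. Only an editorial alignment remains.

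*The statistical harm is small.* Largely true. A reader might expect serious type I error inflation or a general loss of power, and the calculations show neither.

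A separate statistical analysis plan may exist. That does not answer the point, because the protocol itself states the conditional rule and the premise about censoring.

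**Conclusion.** The point holds in this form: the protocol does not fix the test of its binary primary endpoint. Its implied default discards the within-person pairing, and its only matching test is optional and conditional. The condition could not be met in practice under the ordinary meaning of censoring. Under the dropout meaning it is possible but fragile, and can be judged only from the data.

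The defect is mainly one of pre-specification. The conservatism of the log-rank test and its loss of about 4–6 points of power rest on assumed correlation of 0.3–0.6. The power loss also rests on the low-incidence scenario and the chi-square form of McNemar's test. At the planning rates of 65% and 30% the choice barely affects power. All simulated figures ignore period effects and dropout.

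**What to change.** In 3.4, name one primary analysis that does not depend on censoring: the paired comparison, in the intention-to-treat population, of infested versus not infested during each 6-week treatment period, by McNemar's test or its period-adjusted form, at two-sided 5%. State whether the exact or the chi-square form is used.

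Add a rule for participants without a complete second period, for example a paired model that uses incomplete pairs, with McNemar's test on complete pairs as a sensitivity analysis.

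Make time to first infestation supportive, with a method that respects pairing. Delete the no-censoring condition. Either define censoring as dropout or remove the statement that it is not a major issue. In 3.1.2, change the endpoint's time frame from the whole study to each 6-week treatment period, in line with 3.4.

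The cost is wording in 3.1.2 and 3.4. No larger sample is needed: with 68 complete pairs at 65% versus 30%, exact McNemar power is about 98% with independent periods and about 99% at an assumed correlation of 0.2 between the two yes/no outcomes.

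### None of the named efficacy tests uses the randomised sequence or half term: a change in louse exposure costs some power and, only if the sequences complete very unequally, distorts the comparison

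*Protocol*

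**What the plan says.** Sections 2.3.1 and 2.3.3.4 randomise participants 1:1 to an order, active first or placebo first, with six weeks on each product. Section 3.4 (Analytical Methods) names three efficacy tests:

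- **Time to first infestation:** Kaplan-Meier curves and a log-rank test by treatment.
- **Infested or not:** McNemar's "test on these binary outcome (evidence/no evidence of active head louse infection during the treatment period) data as a simple method". It is offered as a possible addition, for the case that no censoring occurs.
- **Number of infestations:** "the Wilcoxon signed rank test will be used for the paired data derived from the time spent in each arm of the study". No condition is attached.

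None has a term or stratum for sequence or half term. In its place the section states two assumptions. The individual's "risk remains more or less constant over the relatively short time of the study", and the case-number estimate "assumes that the potential rate of contact and reinfestation is more or less linear". The planned check of infestation at entry and at the start of the wash-out compares the arms; it adjusts no efficacy test.

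**The concern.** Using each person as his or her own control removes differences between people. It does not remove differences between half terms. Louse exposure could plausibly change in a study expected to run from September to January, and nothing in the document shows that it will not.

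Two things follow if it does change. With equal completion, the half-term difference adds noise that the paired tests count as random, so they lose power. With unequal completion, part of the half-term difference enters the treatment comparison. Section 3.4 itself expects that any right censoring would come from the second half term. Section 2.3.7 allows withdrawal for lack of efficacy, which could fall unevenly on the two sequences.

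**Working it through.** **1. The plan's own figure.** Inputs from section 3.4: alpha 0.05, power 80%, "anticipating the expected non-infestation rates to be 65% for Octanediol 1% Solution and 30% for the placebo". Freedman's log-rank formula, two-sided:

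- HR = ln(0.65)/ln(0.30) = 0.358
- Events = (1.96 + 0.84)² × ((1 + 0.358)/(1 − 0.358))² = 35.1
- N = 2 × 35.1/(2 − 0.30 − 0.65) = 66.8, so 67 in total

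This matches the table and the statement that "the required sample size is therefore estimated as 34 subjects per treatment". The section also gives a lower-incidence scenario: "the possible number of new cases would be 24 over the 6 weeks of one half term, or 12 cases per treatment" without any effect, and 5 on active. That is 12/34 = 35% against 5/34 = 15% infested.

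**2. Why half term matters.** On an additive scale, let τ be the treatment effect, π the change from half term 1 to half term 2, and d the outcome on active minus the outcome on placebo. The mean of d is τ − π for active-first and τ + π for placebo-first. Pooled over n₁ active-first and n₂ placebo-first completers:

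mean d = τ + π × (n₂ − n₁)/(n₁ + n₂)

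The share of π that enters the comparison, by size of imbalance:

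- 34/34: 0
- 34/29: 5/63 = 0.08
- 34/26: 8/60 = 0.13
- 34/24: 10/58 = 0.17
- 34/20: 14/54 = 0.26

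With equal numbers there is no bias, but the pooled spread of d contains π², so the tests become conservative. Comparing half term 1 minus half term 2 between sequences gives (τ − π) − (−τ − π) = 2τ. There π cancels for any n₁ and n₂.

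**3. Equal completion, power** (simulation, 100,000 runs; 12 against 5 cases per 34; no person effect; half-term odds ratio assumed):

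| Half-term OR | McNemar (chi-square) | Prescott |
|---|---|---|
| 1 | 0.81 | 0.80 |
| 2 | 0.79 | 0.80 |
| 3 | 0.77 | 0.79 |
| 5 | 0.72 | 0.79 |
| 8 | 0.66 | 0.77 |

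With the half-term effect set as a threefold hazard ratio, McNemar has size 0.031 and power 0.77, against 0.80 for Prescott. At the 65%/30% rates the loss is under 1 point at OR 3 and 2-7 points at OR 8, because power is already high.

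For counts (2,000 runs), signed rank against rank-sum by sequence, frailty variance 0 and then 1:

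- HR 2: 0.79 v 0.79, 0.74 v 0.72
- HR 3: 0.77 v 0.81, 0.70 v 0.73
- HR 4: 0.80 v 0.85, 0.69 v 0.72

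The rank-sum gain therefore appears only from about a threefold difference.

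**4. Type I error at an assumed threefold difference** (OR 3 for McNemar and Prescott, HR 3 for the count tests; ranges run over the person-effect settings and, for the binary tests, both rate scenarios):

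| Completers | McNemar (chi-square) | Prescott | Signed rank | Rank-sum by sequence |
|---|---|---|---|---|
| 34/34 | 0.037-0.041 | 0.049-0.050 | 0.010-0.014 | 0.043-0.053 |
| 34/29 | 0.044-0.047 | 0.048-0.050 | – | – |
| 34/24 | 0.061-0.062 | 0.049 | 0.056-0.076 | 0.048-0.055 |
| 34/20 | 0.082-0.093 | 0.049-0.050 | 0.152-0.175 | 0.044-0.046 |

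Simulation error for the count tests is about √(0.05 × 0.95/2,000) = 0.005. At 34/26 and a threefold hazard, chi-square McNemar is 0.051-0.054 and exact McNemar 0.029. A separate run of the signed rank test at 34/29 and 34/26 also showed no inflation. How conservative it becomes at 34/34 depends on the infestation rate assumed. Exact McNemar stays below 0.05 at 34/24. The pooled log-rank is at most 0.053 at 34/24 and 0.03-0.08 at 34/20.

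**5. Power with 34/24 completion, threefold hazard.** McNemar gives 0.53 or 0.83 depending on which sequence loses people; Prescott gives 0.70-0.73.

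**The case against.** The strongest reply is that 1:1 randomisation of order already protects the tests: with balanced completion they hold their level whatever happens to exposure. That is right, and only efficiency remains in that case. The loss is small unless the change is large, and no document supports a particular change.

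A reader might go further than the evidence in three ways:

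- **That type I error is inflated in general, or for McNemar in particular.** McNemar is planned only when nothing is censored, so losing participants removes the condition for using it. The log-rank, planned for that case, is hardly affected at 34/24. Inflation concerns mainly the signed rank test, and needs a gap of about 10 in 34.
- **That clearing whole households at entry must change later exposure.** Section 1.4 treats participants only and offers treatment to infested household members; section 2.3.3.2 extends that offer to any point in the study. Section 3.4 says the others in the house remain a possible source of reinfestation. Participants are cleared again at cross-over.
- **That the log-rank must be stratified by half term.** This gained 1-5 points of power, but it compares different people within each half term and so gives up the self-control for which the cross-over was chosen. It is optional, and a detail that an analysis plan may settle.

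What survives is that section 3.4 names the tests, states the signed rank test without condition, and covers half-term differences by assumption alone.

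**Conclusion.** The point holds as a modest weakness of the stated analysis. It is no evidence that the trial's error rate is out of control.

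- **Equal completion:** McNemar and the signed rank test are valid but conservative. McNemar's loss is about 2-3 points of power at an assumed threefold hazard difference, and 6-12 points only at half-term odds ratios of 5-8 in the 12-against-5 scenario.
- **Markedly unequal completion (34/24, threefold):** type I error of about 0.06-0.07 for the signed rank and chi-square McNemar tests, and power that rises or falls with the sequence that loses people.
- **Mild imbalance (34/29 or 34/26):** no material inflation.

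All of these sizes rest on assumed half-term effects, completion splits and between-person variation. The direction of the effects follows from the design and does not depend on those choices.

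**What to change.** Change the wording in section 3.4:

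1. For the paired binary outcome, use Prescott's sequence-based test in place of McNemar.
2. For the number of infestations, compute half term 1 minus half term 2 for each participant and compare the two sequences by Wilcoxon rank-sum, in place of the signed rank test.
3. Report infestations by sequence and half term, so that any change in exposure and any imbalance in completion can be seen.

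Stratifying the log-rank by half term may be added but is not required.

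Cost: if exposure is in fact constant, about 1 point of power for the binary outcome (0.81 to 0.80) and about 1.5-3 points for the counts (0.777 to 0.762, or 0.776 to 0.744 with frailty). No change to sample size, visits or data collection is needed. Like the tests they replace, these assume no carry-over between half terms.
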